### 3. Data collection and management

A detailed description of data collection and management is described in the protocol paper. Data collection procedures will be identical in the ICUs assigned to control and to intervention arms, following 1) At ICU admission, including date and hour of admission,

demographic variables, SAPS 3 and SOFA score, reason for admission, comorbidities, functional status, organ support, among others; 2) Data regarding data to ascertain secondary and tertiary outcomes will be collected daily, including documented treatment goals from the DMR; 3) Upon ICU discharge, data on date and time of ICU discharge, place of discharge, and outcome; 4) And finally, at hospital discharge, date and time and outcome.

Trained health care workers collected data, without any involvement of the study committees and investigators. We developed standard CRFs for the trial, with extensive validation and piloting aiming to achieve clarity and consistency. Data was imputed using electronic CRFs in the Research Electronic Data Capture system (REDCap®, USA) via Internet and hosted on a server at the Hospital Israelita Albert Einstein/São Paulo - Brazil.

Data from the intervention arm regarding adherence to the intervention was collected. The main indicators for adherence to the intervention were defined as:

- a. DMR rate per site/bed/day and DMR duration (including individual and periodic feedback to each tele-intensivist).
- b. Rate of recommendations made and validated (accepted and not accepted)/DMR.
- c. Monthly meeting on performance indicators reports: tele-intensivists will send monthly reports to study team, including the executive summary (file sent to the leaderships of each study center/intervention arm, before the monthly meeting) and the meeting record file (structured data about highlighted indicators, action plan, responsibility, and due dates).
- d. Access to the clinical protocols: absolute number of accesses to the video-protocols will be provided and followed.

## 4. Statistical methods analysis

### 4.1. General analysis issues

#### 4.1.1. Analysis population

Primary statistical analyses will be performed according to the intention-to-treat principle. Patient outcomes will be analyzed according to the randomization of the ICU each patient was in, regardless of whether or not the intervention was applied in that ICU. The baseline period is defined as the first two months of data collection in each ICU. The period for the evaluation of the intervention will be defined as the day after the randomization, thus patients admitted to the ICUs the next day of randomization are accounted as of the intervention/control period. Primary statistical analysis will also consider the baseline period in the analyses, while patients admitted to some of the ICUs during the “Interstitial” period (between baseline and randomization) will be excluded.

#### 4.1.2. Database locking

All analyses planned in this statistical analysis plan will be conducted only after the database locking. The data management and checks for missing and consistency will be conducted blinded to the ICU code and allocation.

#### 4.1.3. Missing data

We will perform multiple imputation if missing data on core variables is >5%, under the assumption that the missingness pattern is missing at random (MAR) conditional on the observed data. Core variables are defined as the covariates to be used in the main analysis of the primary outcome: SAPS-3 score, type of ICU admission, invasive mechanical

ventilation at ICU admission, number of ICU beds in the baseline, Brazilian region where the ICU is located, ICU performance in the baseline and order of randomization. We will follow the recommended and standard steps for multiple imputation. We will include the outcome and account for the clustered structure of the data. The imputation model will have the covariates used in the main model and auxiliary variables. We will start with 20 imputed datasets and change the number of imputed datasets based on the fraction of missing information (MFI). We will pool the estimates using Rubin's rules. The random number seed will be set to 2605.

For the severity scores, SAPS 3 and SOFA, we will consider “zero points” or “normal values” where data are missing. In case we perform multiple imputation, we will impute the final composite score.

#### 4.1.4. Multiplicity

Pre-specified secondary outcomes and subgroup analyses will not be adjusted for multiple comparisons. They should, therefore, be interpreted as exploratory.

#### 4.1.5. Other issues

We will not compare baseline characteristics between treatment groups with Null hypothesis significance testing (NHST).

We will evaluate the calibration for in-hospital mortality of the SAPS3 score with data from the baseline period. If necessary, we will recalibrate the model for the studied population. All analyses will be performed with program R (3.4.1 version, the version will be updated at the time of analysis).

The TELESCOPE trial has been running during the COVID-19 pandemic. It is likely that the pandemic changed the usual characteristics of the admitted patients, both if an ICU from the TELESCOPE trial becomes a reference for COVID-19 patients or for non-COVID-19 patients. The ICU performance, both at control and intervention arms, could have influenced the decision-makers at the Federal, State and Municipal level to decide on referring an ICU to be COVID-19 or not. As ICU performance is, in this case, post-randomization, we will not adjust for whether an ICU is reference for COVID-19 or not in the analysis, otherwise it will break the randomization. Neither the steering committee nor tele-intensivists were responsible for any decision about an ICU being a reference or not to COVID-19.

#### 4.2. Statistical analyses

We will follow the framework proposed in the literature to optimize the power and properly account for time in cluster parallel randomized trials with baseline period (longitudinal cross-sectional cluster trials). Thus, we will consider the baseline individual data allowing the secular trend to vary randomly across clusters by extending the random-effects components with an interaction between cluster and time period (baseline vs after randomization). This term also allows for the ICC to differ from observations that are made in the same or different time periods and for estimating two ICCs (the “within-period ICC” and the “between-period ICC”) used to estimate the CAC (the ratio of the between-period and within-period ICCs).

##### 4.2.1. Analysis of the primary outcome

The linear mixed model for the primary outcome will be the following:

$$Y_{ijk} = \beta_0 + \beta_1 X_{ij} + \beta_2 j + \beta_3 Z_{ijk} + \beta_4 L_{ij} + \mu_i + \nu_{ij} + \epsilon_{ijk} \quad \text{Equation (1)}$$

for cluster  $i$ , time-period  $j$  and participant  $k$ , where  $X_i$  denotes the trial arm for cluster  $i$  (coded 0 or 1), and  $j$  denotes the time-period in which participant  $k$  in cluster  $i$  is assessed (0 for baseline, 1 for after randomization). The individual error term is assumed to be Normally distributed and independent of  $\nu_{ij}$  and  $\mu_i$ . Random terms are assumed to be Normally distributed, and  $\nu_{ij}$  is assumed independent of  $\mu_i$ .  $Z_{ijk}$  and  $L_{ij}$  are the matrix of covariates at the individual level and unit level, respectively.  $\beta_1$  is the coefficient of interest for the trial, i.e., the estimate for the difference between those receiving the intervention and those in the control group.

For the primary outcome, we will include the index admission of a patient, i.e., we will not include ICU readmissions. The primary outcome – ICU LOS – will be log-transformed to account for the normality of the residuals of the linear mixed model. These two steps (not including readmissions and log-transformation) were used for the power calculations.

We will use the identity link in the model for the primary outcome and the Satterthwaite's degree-of-freedom correction.

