## 2.4. Randomization and masking

After a 2-month observation period (baseline period) in which performance indicators for eligible ICUs were collected without any intervention (with the purpose of obtaining data for randomization, analysis and characterization of the initial ICU status), the ICUs eligible for the study were randomized. The 30 ICUs were randomly assigned to either the intervention group (n=15) or the control group (n=15) using a restricted randomization algorithm that minimizes imbalance between treatment groups across the following baseline covariates at the ICU level:

- 1) number of ICU beds

- 2) mean SAPS 3, in points
- 3) mean ICU length of stay (LOS), in days
- 4) Standardized mortality rate (SMR)
- 5) Standardized resource use (SRU), and
- 6) A two-category dummy indicator for Brazilian region where the ICU is located (regions South and Southeast x regions North/Northeast/Central-West).

We followed all the steps recommended by Carter and Hood during the application of the minimization algorithm. The randomization was performed at three times, including 14 units during the first randomization, followed by 7 and 9 units (Figure 1). We decided a priori to randomize at three times and the number of units at each randomization was pragmatic, allowing for ethical approval and completion of the baseline period, respecting the minimum of eight units during first randomization and minimum of six on subsequent randomizations.

For the first randomization, we followed the steps: 1) the database with the baseline data (2 months) were locked, 2) derivation of the six covariates per unit, 3) run the algorithm, generating the potential combinations of unit's allocation, 4) a random combination of allocations was selected. The order of each unit in the database was randomly sorted before the algorithm, as well as the order of potential allocations. The select allocation was coded as 0 and 1 by the algorithm. To select whether intervention would be 0 or 1, we performed the final simple randomization and 0 was allocated to the intervention arm. For the second and third blocks, we followed the same steps: we entered the baseline data of the previous block with its allocation and the new covariates. The algorithm accounts for the previous block covariates to calculate the new balance between

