#### 4.2.6. Covariate adjustment

We pre-specified that the analyses for the primary and secondary outcomes will be adjusted by covariates in the original protocol, but we did not define which covariates, except the mean ICU LOS at the cluster level. Based on the literature on the determinants of ICU LOS, we will adjust by three patient level covariates and four ICU level covariates:

- 1) SAPS-3 (continuous term),
- 2) Type of ICU admission (3 categories: medical, elective surgical, unplanned surgical),
- 3) Invasive mechanical ventilation at ICU admission (2 categories: yes, no),
- 4) Number of ICU beds in the baseline (continuous term),

- 5) Brazilian region where the ICU is located (2 categories: South/Southeast, North/Northeast/Central-West),
- 6) ICU performance in the baseline (4 categories: most efficient, least efficient, overachieving, underachieving).
- 7) Groups of randomization (3 categories: first, second and third blocks)

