#### 4.2.7. Subgroup analysis for the primary outcome

We pre-specified in the original protocol three subgroups, as follows:

- 1) Type of admission (medical vs. surgical),
- 2) Tertiles of SAPS3 and
- 3) Mechanical ventilation status (invasive MV vs. not-invasive MV).

We now revised their definition for clarification and added three additional subgroups, based on the main research question of the trial and the literature. Thus, the final six subgroups are defined below:

- 1) Type of ICU admission (3 categories: medical, elective surgical, unplanned surgical)
- 2) Tertiles of SAPS 3 score (defined by “ntile(SAPS3,3)”)
- 3) Invasive mechanical ventilation at ICU admission (2 categories: yes, receive invasive mechanical ventilation at ICU admission; no, receive other respiratory support rather than invasive mechanical ventilation or none)
- 4) Age groups (3 categories: 18-39 years, 40-59 years, 60+ years)

- 5) ICU performance in the baseline (4 categories: most efficient, least efficient, overachieving, underachieving)
- 6) Calendar time from the intervention in trimesters (as categorical)

Sub-groups will be analyzed adding an interaction term between the  $X_{ij}$  in Equation (1) and the subgroup of interest, and a term for the fixed effect of the subgroup of interest if it is not already a covariate. The p-value for the interaction will be evaluated by a likelihood ratio test comparing the model without the interaction and with the interaction.

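### Section 4.2.1 defines the treatment regressor as the period-constant trial arm, which contradicts the stated meaning of β1 in a model that includes untreated baseline patients

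*SAP*

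**What the plan says.** SAP 4.2.1 gives a linear mixed model with fixed terms for X_ij, period j (0 baseline, 1 after randomization), patient covariates and unit covariates, plus random terms for cluster and cluster-by-period. The text below the equation defines X_i, not X_ij: it "denotes the trial arm for cluster" i, coded 0 or 1. The same paragraph describes β1 as "the estimate for the difference between those receiving the intervention and those in the control group".

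The rest of the SAP sets the context:
- 2.4: in the two-month baseline, "performance indicators for eligible ICUs were collected without any intervention".
- 4.1.1: "Primary statistical analysis will also consider the baseline period in the analyses", and "The period for the evaluation of the intervention will be defined as the day after the randomization".
- 2.6.2: power was re-estimated for a parallel cluster trial with a baseline period, giving 80% down to a cluster autocorrelation (CAC) of 0.906.
- 4.2.3.1 and 4.2.5 refit Equation (1) for other outcomes, and 4.2.7 adds subgroup interactions with X_ij.

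The SAP nowhere states the value of X for an intervention ICU during baseline.

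**The concern.** An ICU's arm does not change between periods. If X is coded as the words define it, intervention ICUs have the same X at baseline and afterwards, and the separate period term only removes a time trend common to both arms. β1 then estimates one arm difference averaged over two periods, and in the first of these the true difference is zero. The result is neither the post-randomization effect nor the contrast that the SAP says β1 represents.

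Two things would be at stake: a primary estimate pulled toward the null, and loss of part of the precision for which the baseline data were brought into the model. The readiness-for-discharge, patient-level secondary and subgroup models inherit the definition by reference.

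**Working it through.** **Inputs from the SAP.** 15 ICUs per arm; effect 1.5 days; SD 10 and 500 patients per ICU (2.6.1); baseline SD 9.8 and ICC 0.087; cluster-size CV 0.4; CAC threshold 0.906; 500 patients per ICU in each period for the re-estimation (2.6.2). The SAP reports CAC estimates above 0.960 in external data, so 0.906–0.96 is used as the range.

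**Assumptions.** Two-sided alpha. About 56 baseline patients per ICU in two months (500 × 2/18 = 55.6). The covariate-adjusted ICC is not given, so 0.087, 0.05 and 0.018 are shown.

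**Formulas.** For the two period means of one ICU, in units of SD²:
- a = ICC + (1 − ICC)/m0 (baseline variance)
- b = ICC + (1 − ICC)/m1 (post-randomization variance)
- c = CAC × ICC (covariance)

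With equal clusters, generalized least squares gives:
- X switched on after randomization: E(β1) = the true effect; Var = (2/15) SD² (b − c²/a).
- X constant over periods: E(β1) = w × the true effect, with w = (a − c)/(a + b − 2c); Var = (2/15) SD² (ab − c²)/(a + b − 2c).

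**1. The plan's own figure.** SD 10, m0 = m1 = 500, ICC 0.087, CAC 0.906.
- a = b = 0.087 + 0.913/500 = 0.08883; c = 0.07882.
- Switched on: b − c²/a = 0.08883 − 0.06994 = 0.01888; SE = √(100 × 0.01888 × 2/15) = 0.502. With CV 0.4 the SE is 0.508 and power is 81% (t, 28 df) or 84% (normal). This reproduces the stated 80%.
- Arm-constant: w = 0.5, so E(β1) = 0.75 days. When a = b the variance factor is (a + c)/2 = 0.08382; SE = √(100 × 0.08382 × 2/15) = 1.057. Power = Φ(0.75/1.057 − 1.96) = Φ(−1.25), about 10–11%. CV 0.4 leaves it at about 10%.
- Post-randomization data alone: SE = √(100 × 0.08883 × 2/15) = 1.088; power 28% (normal) or 26% (t).

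Of these three, only the switched-on coding matches 2.6.2.

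**2. A two-month baseline.** SD 9.8, m0 = 56, m1 = 500, ICC 0.087, CAC 0.906.
- a = 0.087 + 0.913/56 = 0.10330; b = 0.08883; c = 0.07882.
- w = 0.02448/0.03449 = 0.71, so E(β1) = 1.07 days instead of 1.5.
- Arm-constant SE = 1.049; power = Φ(1.065/1.049 − 1.96) = 17%. Switched-on SE = 0.606; power 70%.
- At CAC 0.96: w = 0.01978/0.02509 = 0.79; power 20% against 82%.

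**3. Across ICC values.** m0 = 56, CAC 0.906–0.96; shares for equal clusters, power with CV 0.4 and t on 28 df.

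| ICC | Share of effect kept | Power, arm-constant X | Power, switched-on X |
|---|---|---|---|
| 0.087 | 71–79% | 17–19% | 65–78% |
| 0.05 | 77–83% | 28–32% | 78–86% |
| 0.018 | 84–87% | 68–71% | 95–96% |

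With 30 to 100 baseline patients per ICU the share ranges over 63–87% at ICC 0.087 and 76–93% at ICC 0.018.

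**4. Allowing for baseline performance.** The planned model adjusts for baseline ICU performance, which is built partly from length of stay. A rough simulation (ICC 0.087, CAC 0.93, 56 + 500 patients, performance proxied by a median split of baseline length of stay) cut the arm-constant SE from about 1.05 to about 0.73. Power was roughly 28–35% against about 75% switched on. The dilution remained, with about 70% of the effect kept.

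**The case against.** The strongest reply is that the intent is already fixed. X_ij is printed in the equation and again in 4.2.7, β1 is described in terms of receiving the intervention, the baseline was untreated, evaluation starts after randomization, and the power framework requires a switched-on indicator. The missing j in the definition may be only a typographical slip. A competent analyst would code it correctly.

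Most of this stands, and it is why the harm is conditional. It does not remove the error. With the j restored, the words would still define X as the arm of the cluster. The printed subscript does not settle the matter alone, because L_ij also carries ij while the unit covariates listed in 4.2.6 (baseline beds, region, baseline performance, randomization block) are fixed for each ICU. That is loose notation rather than a second fault, but it means ij cannot be relied on to signal variation by period.

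A second reply is that the power figures are not for the planned model, which uses log length of stay and adjusts for covariates. This is correct. The SAP gives no log-scale ICC or CAC, and step 4 shows that baseline performance recovers part of the precision.

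A reader might go further and infer that the wrong model will be fitted, or that the trial's real power is 10–20%. The documents support neither. The first needs a programmer to follow the definition against the equation and the stated meaning of β1. The second carries unadjusted day-scale figures over to a model that the SAP does not plan.

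**Conclusion.** The definition of X in 4.2.1 is wrong as worded. It conflicts with the meaning given to β1 in the same section and with the basis of the 80% power in 2.6.2. The intended post-randomization indicator can be inferred, so this is a definition to correct before analysis, not evidence of a wrong analysis.

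If the wording were coded literally, β1 would mix a null baseline contrast with the real effect and keep roughly 70–87% of it, with a material loss of power. The loss is large at the unadjusted ICC and moderate if covariates bring the ICC down to 0.018. In either case it is smaller than the unadjusted figures suggest. The share kept does not depend on the SD, but it does depend on the ICC, the CAC and the assumed baseline cluster size, and covariate adjustment would change it.

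**What to change.** In 4.2.1, replace the definition of X_i with: *X_ij = 1 only for patients in intervention-arm ICUs in the post-randomization period (j = 1), and 0 for all baseline patients and all control-arm patients; β1 is the post-randomization intervention effect.* State that the same coding applies wherever Equation (1) is reused (4.2.3.1, 4.2.5 and 4.2.7).

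The sentence also settles the direction of the contrast: 2.4 codes allocation as 0 for intervention and 1 for control, while 4.2.1 does not say which arm is 1.

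The cost is one sentence. It agrees with the printed equation and the power basis and needs no further data. Section 1 states that no analysis had yet been undertaken, so the change can be made without reference to results.

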#### 4.2.2. Per protocol analysis for the primary outcome

We are planning a sub-study to evaluate a per-protocol analysis in the TELESCOPE trial. We will use the principles of causal inference and deal with post-randomization

confounding and biases, keeping the inference based on the randomization. We plan to use the principal stratification approach.

#### 4.2.3. Sensitivity analyses for the primary outcome

These two sensitivity analyses regarding the primary outcome were pre-specified in the original protocol.

##### *4.2.3.1. Readiness for discharge*

The primary outcome – ICU LOS – is an outcome that depends also on factors outside the ICU for those that improved during the ICU stay, such as ward bed availability. For this reason, we specified to also measure the ICU LOS in terms of readiness for discharge, i.e., days from ICU admission to the first day the attending team defined the patient was ready to be discharged alive. This variable was measured during the daily collection data and will be measured as counts, because we will not have time accuracy for its measurement. The attending clinicians were not aware that this would be an outcome of the TELESCOPE trial. We will fit the Equation (1) using generalized linear mixed models to accommodate it using a Poisson or negative-binomial family with a log link.

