## 2.5. Outcomes

### 2.5.1. Primary outcome

At an individual level, the primary outcome of this trial is ICU length of stay, measured in days, taking into account the time interval in hours between patients' ICU admission and ICU discharge times (i.e., transfer to another care facility or another hospital) or ICU death, as defined by the hospital's system date and time. Date and time will be entered by the health care worker responsible for data collection. ICU LOS will be derived in 24h periods with decimal places, as recommended.

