##### *4.2.3.2. Competing risk of death*

The primary outcome – ICU LOS – is subject to the competing risk of death. Therefore, the ICU LOS represents a composite summary of two process: time to ICU discharge alive and time to ICU death. There are alternatives to deal with this scenario, such as 1) fitting competing risk models, modeling time to discharge alive and consider time to ICU death as a competing event, 2) analyzing LOS separately between ICU survivors and

non-survivors, 3) weighting differently the LOS for those who died, among others. As expected, the potential different results on the primary outcome analysis will likely occur or be relevant only if the intervention has an effect on mortality. We consider this a secondary analysis because, *a priori*, we did not expect a major impact of the intervention on mortality. In this sensitivity analysis, we will use the competing risk framework, presenting the analysis with cause-specific hazard ratios and sub-distribution hazard ratios for the time to discharge alive. The models will be adjusted for the same six covariates as the primary analysis, and the baseline period will be accounted as the mean ICU LOS at the unit level in the baseline period. We will account for the correlated data structure with a “shared frailty model”.

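### The readiness-for-discharge sensitivity analysis changes the summary measure, and possibly the patients, along with the end of the stay, and no planned fit separates these changes

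*SAP*

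**What the plan says.** **Primary analysis.** SAP 2.5.1 measures ICU stay from admission to ICU discharge or ICU death: "ICU LOS will be derived in 24h periods with decimal places". SAP 4.2.1 says that it "will be log-transformed to account for the normality of the residuals of the linear mixed model", and adds: "We will use the identity link in the model for the primary outcome". The exponentiated arm coefficient is therefore a ratio of geometric means.

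**Readiness analysis.** SAP 4.2.3.1 gives as its reason that ICU stay "is an outcome that depends also on factors outside the ICU for those that improved during the ICU stay, such as ward bed availability". The alternative outcome is "days from ICU admission to the first day the attending team defined the patient was ready to be discharged alive". It "will be measured as counts, because we will not have time accuracy for its measurement". Equation (1) is then refitted as a generalized linear mixed model "using a Poisson or negative-binomial family with a log link". The exponentiated coefficient is here a ratio of arithmetic means.

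**Deaths.** SAP 4.2.3.2 recognises that "the ICU LOS represents a composite summary of two process: time to ICU discharge alive and time to ICU death". SAP 4.2.3.1 does not say how a patient who dies in the ICU without being declared ready enters the readiness analysis.

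**Reporting.** The table in SAP 5.1.4 places readiness beneath the primary result, as a sensitivity analysis of how the primary outcome is defined. It gives unadjusted mean (SD) for both outcomes by arm and period. The column for the type of effect estimate holds a placeholder in both rows.

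**The concern.** A sensitivity analysis of an outcome definition is read by comparing its result with the primary one. Here the intended change is where the stay ends: at actual discharge or at readiness. Three other things may move with it:

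- the unit, from decimal days to whole days;
- the summary measure, from a geometric-mean ratio to an arithmetic-mean ratio;
- the patients, if ICU deaths without readiness drop out.

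The geometric mean reflects typical stays, while the arithmetic mean is pulled by long ones. If rounds act mainly on long stays, the readiness ratio can show a clear reduction beside a primary ratio near 1 even when nobody waited for a ward bed. If they act mainly on short stays, the pattern reverses. Agreement between the two rows can also be accidental. Either way, comparing the rows does not show how much the definition matters.

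**Working it through.** The SAP gives no figure for this comparison, so there is none to reproduce. The check asks how far the two ratios can differ on the *same* stays with *no* discharge delay.

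**Inputs from the SAP:** baseline mean 7.8 and SD 9.8 days (2.6.2); planning mean 8, SD 10 and a reduction to 6.5 days, a ratio of 6.5/8 = 0.8125 (2.6.1); truncation at 90 days (2.5.3).

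**Assumptions, not in the SAP:** a log-normal shape and the effect patterns below. Clustering and covariates are left out.

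**1. Closed form, baseline figures, no truncation.**

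- Log variance: ln(1 + (9.8/7.8)²) = ln(2.579) = 0.947, so log SD s₀ = 0.973.
- With the median unchanged, the geometric-mean ratio is 1.00 and the arithmetic-mean ratio is exp((s₁² − s₀²)/2).
- For s₁ = 0.90 s₀: exp(−0.19 × 0.947/2) = exp(−0.090) = 0.914.
- For s₁ = 0.95 s₀ and 0.85 s₀, the same formula gives 0.955 and 0.877.

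In the middle case mean stay really falls, from 7.8 to about 7.8 × 0.914 = 7.1 days. The count model reports that correctly, and the log model correctly reports an unchanged median. Neither is biased; they summarise one change differently.

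**2. Simulation, planning figures.** Four million log-normal stays with mean 8 and SD 10, capped at 90 days:

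| Effect pattern, no delay | Geometric ratio | Arithmetic ratio |
|---|---|---|
| All stays × 0.8125 | 0.81 | 0.81 |
| Only days beyond day 7 shortened (by 46%) | 0.92 | 0.81 |
| Only days beyond day 14 shortened (by 91%) | 0.94 | 0.81 |
| Only stays under 4 days shortened (by 30%) | 0.86 | 0.97 |

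The first three rows all have the same mean reduction of about 1.5 days. Counting whole days matters little: an arithmetic ratio of 0.81 becomes 0.80 when days are rounded down and 0.82 when rounded up.

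**3. A real delay, for scale.** Let the simulated stays be times to readiness, with a proportional effect of 0.8125 and a 1-day wait for every patient in both arms:

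- readiness, arithmetic ratio: 0.81;
- actual stay, geometric ratio (the primary summary): 0.85;
- actual stay, arithmetic ratio (the comparison missing from the plan): 0.83.

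The planned comparison is 0.85 against 0.81. With the summary measure held fixed it is 0.83 against 0.81, so under half of the planned gap (0.850 − 0.833 out of 0.850 − 0.8125) comes from the change of summary. In step 2, with no delay at all, the gap reaches 0.92 against 0.81. The change of summary can therefore produce a larger gap than a genuine 1-day delay.

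**The case against.** **Both models work on the log scale.** The primary model has an identity link on log stay and the readiness model has a log link, so both exponentiate to ratios. A reader might infer a switch from a difference in days to a ratio; the text does not support that. Under the effect that Equation (1) itself describes, one shift in log stay with a common residual variance, the two ratios coincide. This stands: divergence requires an effect that is not proportional. The SAP does not claim that proportionality will hold, however, and a sensitivity analysis should not depend on it.

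**Changing the definition is the purpose.** This also stands, and the change of endpoint is no fault. The issue is what changes with it.

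**The SAP never says that a gap will be read as ward-bed delay.** Correct. A reader might infer that the plan commits to that attribution, but it only gives outside factors as the reason for measuring readiness. Still, that is its only stated reason, and the table invites the comparison.

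**The count model has a stated justification.** Readiness lacks clock time. That explains the model for readiness, but does not prevent fitting the same model to actual stay in whole days.

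**The effect table already shows arithmetic means for both outcomes.** In the no-delay illustration a reader would see mean stay fall alongside mean readiness time. This is a useful but partial check: the means are unadjusted, carry no interval for the contrast, and may cover different patients.

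**The competing-risk analysis in SAP 4.2.3.2 addresses deaths.** It yields hazard ratios for discharge alive, so it does not link the two definitions.

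**Conclusion.** The point holds as a minor one. As planned, a difference between the readiness result and the primary result mixes the change of definition with a change from geometric-mean to arithmetic-mean ratio, and possibly with a change of patients. Illustratively, the summary measure alone gives 1.00 against 0.91 for a 10% smaller log SD, or 0.92 against 0.81 when only days beyond day 7 are shortened. These sizes rest on the assumed log-normal shape and on effect patterns chosen for illustration; the gap vanishes under a homogeneous proportional effect.

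Two stronger readings are not supported. One is that the readiness model would manufacture a spurious benefit: in the illustrations the mean stay truly shortens. The other is that the analysis is invalid or that the primary inference is affected: the readiness ratio is a legitimate summary of its own outcome, and the primary analysis stands apart from it.

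**What to change.** - In SAP 4.2.3.1, add a fit of the same count model of Equation (1), with the same family, periods and covariates as for readiness, to actual ICU stay in whole days. Use the same patients as the readiness analysis and count days in the same way.
- State which patients these are, and how those who die in the ICU without being declared ready are treated.
- Report the result as an added row in the table of SAP 5.1.4. Replace the placeholder by the ratio type in each row (geometric-mean or arithmetic-mean ratio).
- Say that any statement about discharge delay will rest on the two count-model ratios, not on readiness against the primary estimate.

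Log-transforming readiness days to match the primary model is not a good substitute. It is undefined for zero counts, and the SAP does not say whether counting starts at 0 or 1.

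The cost is one extra model fit and one table row. No new data are needed, and the primary analysis is unchanged.
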